This interface will include data on both ICS and SABA inhaler use. The interface will also have flags to notify the office of under or overuse of inhalers, with a protocol in place to reach out to patients. We will also be assessing the factors associated with the feasibility and sustainability of the Remote Health Management Platform by the healthcare team. This will be done by weekly contact with the healthcare team, rapid cycle improvement of the web portal, and written assessments. Follow-up assessments through interview will be conducted at the end of the trial with health providers.

[figure not shown]

Figure 1. Study Arms

Participant Sites

The participant sites will be pediatric clinics in the Chicagoland Area. Each site in this proposed study has a strong history of research collaborations with [name], which includes the ability to recruit and retain patients in research studies.

We will be recruiting from at least four of the following sites:

- Children’s Healthcare Associates
- Chicago Family Asthma and Allergy
- Clark/Deming Resident Clinic (Lurie Children’s)
- Pulmonary Clinic (Lurie Children’s)
- Lurie Children’s Uptown Clinic

Study Design and Procedures

1. **Design:** We will conduct a randomized controlled trial comparing asthma inhaler use and asthma-related outcomes between children who either receive the Remote Health Management Platform (intervention) or Standardized Education (control) for asthma management. We will use a prospective cohort design to determine the effect of the intervention on the aforementioned outcomes.

We will enroll patients from Chicago pediatric clinics, as well as inpatient units at Lurie Children’s Hospital. At enrollment, we will randomize children to either the Remote Health Management Platform (intervention) group or the Standardized Education group (control).

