- b. Health providers will be interviewed about their experience using the web portal (Study Aim 3), using the data generated by the sensors, and managing pediatric asthma patients and their interaction with parents
- e. Health providers will be informed that the in-person, or telephone, interview will be audio-recorded. In-person interviews will be conducted at their clinic location in a private office.
- f. Interviews will last approximately 60 minutes and conducted by research staff.

Study Extension

Data analysis will begin 12 months after a participant is enrolled (beginning January 2018.). During the analysis period, we will also determine the feasibility of implementing the intervention more broadly throughout the healthcare system.

Study Subjects:

Eligible participants will be children 4-17 years old with moderate or severe persistent asthma, as diagnosed by their pediatrician, who are primarily seen for their asthma care at one of the participating clinical sites, and who have parents/caregivers willing to participate in this study. Participants will also be required to have received oral corticosteroids in the past year.

Study Enrollment:

Recruitment will occur by a research assistant at all sites. Scheduling of recruitment and participant screening will require the healthcare team to identify potential participants and then the RA either calling or mailing an informational pamphlet to the parents prior to their next appointment. Participants may also be recruited in the clinic by the RA, but will require the RA to follow-up with them via the telephone to properly install and utilize the Remote Health Management Platform. Participants may also be recruited through Lurie Children's Hospital Inpatient service after an asthma exacerbation. Only children who receive their primary care from one of the 5 study clinics will be permitted to be in the study. A member of the research team will work with hospitalists to recruit these individuals.

For the post-trial semi-structured interviews, only those participants who had previously responded that they were interested in further contact by the research team will be recruited. Study staff will contact potential participants for interviews by telephone and only schedule a time if participants remain interested after the interview study has been explained to them.

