- *Clinical management*: To compare clinical management, data on physician-patient communication and rates of follow up will be obtained from the web portal for all patients for a year for each intervention participant. This will be measured via the number of tasks have been completed. Additionally, in the Intervention group, we will work with physicians to conduct rapid-cycle improvements to the web portal interfaces, through conversations the RA and the PI have with clinicians. We will also follow up with healthcare team to ensure follow-up calls are occurring. Finally, a four-question survey of members of the healthcare team about the acceptability and feasibility of the sensor will be conducted periodically.

Statistical Analysis:

Demographic and baseline characteristics:

Demographic and baseline characteristics including gender, age, race, ethnicity, and co-morbidities will be summarized for each treatment group and overall. The demographic and baseline characteristics summary will be based on all randomized subjects.

Baseline values for efficacy parameters (*ACT*, quality of life score, *PAMSE*) will also be presented for each treatment group and overall based on all randomized subjects.

For continuous variables, non-missing will be used to calculate the mean, median, SD, IQR, minimum and maximum by treatment group and overall. For categorical variables, the count and percentages of each possible value will be tabulated by treatment group and overall.

All comparisons of baseline characteristics between treatment groups will be adjusted for potential household clustering using robust standard errors. For continuous variables, comparability of treatment groups will be assessed using general linear models. For discrete variables, comparability will be assessed using the Cochran-Mantel-Haenszel general association test. P-values will be displayed as descriptive statistics of comparability in order to identify potential baseline imbalances with an alpha level of 0.05.

AIM 1. Determine factors influencing clinical and psychosocial outcomes.

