After the patient's enrollment visit, parents will be contacted via email or phone at 1, 3, 6, 9, and 12 months to complete a REDCap survey. Each quantitative survey item will be summarized using descriptive statistics such as frequencies and percentages along with any corresponding measures of spread. Qualitative data will be coded and analyzed by theme analysis.

The following questions will be asked:

Quantitative Questions:

1. How often do you check the sensor system?
 - More than once a daily
 - Daily
 - Once a week
 - More than once a week
 - Every other week
 - I don't check the Propeller Sensor (*If selected, participants will only answer question 1 and 5*)
2. How often in the past week did you receive useful asthma information through the sensor system?

- Once
 - Twice
 - Three or more times
 - I did not receive useful asthma information through the sensor system
3. How helpful is the sensor system in managing your child's asthma?
- Extremely helpful
 - Very helpful
 - Helpful
 - A little helpful
 - Not helpful
 - I have not checked the sensor system
4. What do you enjoy most about the sensor system?
- Easy to use
 - Ability to track inhaler use
 - Asthma Education cards
 - Other: *fill in the blank*
 - Nothing
5. Do you have any issues regarding the sensor system?
- *Comment Box*

AIM 3. Improve management by physician and clinical team.

On a biweekly basis, we will collect quantitative data from clinics on the number of time physicians' follow-up with patients and the follow-up outcome. The research team will know exactly how many alerts physicians are receiving, and how physicians are following-up with patients from the Propeller dashboard. The data from the Propeller dashboard will be summarized with descriptive statistics. Clinicians will also be contacted at 1, 3, 6, 9, and 12 months through REDCap surveys to determine if the data is helping them with management and aspects of the platform they like and dislike. Qualitative data will be coded and analyzed by theme analysis.

The following questions will be asked:

Quantitative Questions:

1. In the past week, how many times did you check the propeller dashboard?
 - Once time
 - Twice
 - 3 or more times
 - Zero
2. Are the Propeller Dashboard flags useful to you?
 - Yes
 - No
3. In the past week, how many times did you have to follow-up with patients due to alerts you received regarding the over use of Albuterol?
 - Once
 - Twice
 - 3 or more times
 - Zero

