- Proventil HFA
- Ventolin HFA
- Xopenex

Supported Controller/Daily Medications:

- Advair HFA
- Advair Diskus
- Asmenex
- Combivent Respimat
- Dulera
- Flovent Diskus
- Flovent HFA
- QVAR
- Serevent Diskus
- Spiriva Respimat
- Striverdi Respimat

Timeline

Pilot: November 2016

- Pilot group of 8-10 families

Phase 1: Enrollment

- December 2016-December 2017
- Collect EMR data from the previous year
- Randomization

Phase 2: Intervention

- December 2016-December 2018
- Intervention Group will have the Remote Health Management device for 1 year
- Standardized Group will receive enhanced, standardized asthma education
- Each group will fill out the following surveys 5x during the study period:
 - ACT
 - PAMSE
 - PACQLQ
 - iTRACC Survey (Control Arm) or Intervention Survey (Intervention Arm)
 - Number of hospitalizations, ED visits, exacerbations
- We will pull information from the EMR to determine oral corticosteroid use

Phase 3: Analysis

- January 2018- December 31, 2018
- All data analyzed
- Preparation and submission of academic abstracts and papers

- Help to prepare for full scale rollout, if applicable
- Semi-structured interviews of subsample of participants
- Semi-structured interviews of health providers in the trial

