# Missing data and sensitivity analyses:

Missing data will be handled using Multiple Imputations. Sensitivity analyses will be conducted using SAS procedures PROC MI and PROC MIANALYZE. Other sensitivity analyses may be performed if appropriate.

AIM 2. Enhance parental management through improved inhaler use.

After the patient's enrollment visit, parents will be contacted via email or phone at 1, 3, 6, 9, and 12 months to complete a REDCap survey. Descriptive statistics (frequencies and percentages) of each quantitative question will be summarized at each time point and associations between outcomes and demographic predictors will be analyzed by Chi-squared test. Qualitative data will be coded and analyzed by theme analysis.

AIM 3. Improve management by physician and clinical team.

On a biweekly basis, we will collect quantitative data from clinics on the number of time physicians' follow-up with patients and the follow-up outcome. The research team will know exactly how many alerts physicians are receiving, and how physicians are following-up with patients from the Propeller dashboard. The data from the Propeller dashboard will be summarized and associations between outcomes and clinic predictors will be analyzed by Chi-squared test. Clinicians will also be contacted at 1, 3, 6, 9, and 12 months through REDCap surveys to determine if the data is helping them with management and aspects of the platform they like and dislike. Descriptive statistics (frequencies and percentages) from surveys will be summarized at each time point and associations between outcomes and clinic predictors will be analyzed by Chi-squared test.

Qualitative data will be coded and analyzed by theme analysis.

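### SAP Aim 3 plans an ordinary chi-squared test on repeated dashboard data from four or five clinics, with no unit of analysis or clustering adjustment, where the Protocol plans description only

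*SAP*

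**What the plan says.** SAP, Aim 3, describes the data: "On a biweekly basis, we will collect quantitative data from clinics on the number of time physicians' follow-up with patients and the follow-up outcome". It then sets the analysis: "The data from the Propeller dashboard will be summarized and associations between outcomes and clinic predictors will be analyzed by Chi-squared test". It does not say what one observation is, whether the rounds are collapsed over time, how counts of follow-ups become categories, or what a clinic predictor is. The neighbouring sentence on clinician surveys works at each time point; the dashboard sentence has no such limit.

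Protocol, Aim 3 under Statistical Analysis, plans no test for the same data: "The data from the Propeller dashboard will be summarized with descriptive statistics".

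The number of clinics is small. Protocol, Participant Sites: "We will be recruiting from at least four of the following sites", followed by a list of five. Protocol, Study Enrollment: "Only children who receive their primary care from one of the 5 study clinics will be permitted to be in the study". The observation period is long. Protocol, Timeline: "Intervention Group will have the Remote Health Management device for 1 year". Under Secondary Outcomes, the clinical management item says that "data on physician-patient communication and rates of follow up will be obtained from the web portal for all patients for a year".

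Elsewhere the SAP does allow for correlation. Baseline comparisons use standard errors robust to household clustering, and the Aim 1 models carry random effects of family and clinic.

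**The concern.** A chi-squared test takes its variance from the number of independent observations. Records from the same child, clinician or clinic over a year are likely to be alike. A predictor that is constant within a clinic is also constant within each child in it, so positive correlation makes the test statistic too large and the p-value too small. The SAP's authors expected clinic and family correlation in Aim 1, but they state no allowance for it in Aim 3, where clinic is itself the subject.

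At stake is a possible false association between clinic features and follow-up behaviour in a secondary process measure. In addition, the two documents disagree on whether these data are tested at all.

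**Working it through.** **1. Inputs from the documents.** 125 patients per arm, 20% dropout and a two-sided 5% level (Protocol, Sample Size Determination; no level is set for Aim 3). Four to five clinics (Participant Sites, Study Enrollment). One year of device use (Timeline).

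**2. Assumptions, because the documents give no figure.** Biweekly means every two weeks, so 26 rounds a year. Each intervention child contributes one record per round, children are spread evenly over clinics, and the predictor has two levels (1 degree of freedom). The ICCs are assumed and shown as a range.

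**3. The plan's own figure.** There is none for Aim 3. The arm size used below does reproduce: n per arm = (1.960 + 1.036)² × [1/(0.545 × 0.455) + 1/(0.75 × 0.25)] / 0.9181² = 99.8, and 99.8/0.8 = 124.7, so 125. Five clinics give 125/5 = 25 children each, and 25 × 26 = 650 records per clinic. The 100 children left after 20% dropout, in four clinics, give the same 25 and 650.

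**4. Formula.** Design effect DE = 1 + (m − 1) × ICC, with m records per cluster. True type I error of a nominal 5% test = P(χ²₁ > 3.84/DE).

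**5. Results.**

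| Setting | m | ICC | DE | Type I error |
|---|---|---|---|---|
| Pooled, correlation within patient | 26 | 0 | 1.00 | 5% |
| same | 26 | 0.01 | 1.25 | 8% |
| same | 26 | 0.05 | 2.25 | 19% |
| same | 26 | 0.10 | 3.50 | 30% |
| Clinic-level predictor, one record per patient | 25 | 0.01 | 1.24 | 8% |
| same | 25 | 0.05 | 2.20 | 19% |
| Clinic-level predictor, pooled records | 650 | 0.001 | 1.65 | 13% |
| same | 650 | 0.01 | 7.49 | 47% |

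With pooled records and clinic ICC 0.01, 100 children in five clinics (m = 520, DE 6.19) give 43%, and 125 in four clinics (m = 812.5, DE 9.12) give 52%.

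A beta-binomial simulation (five clinics of 25 patients, outcome prevalence 0.30, 4,000 runs per setting) agrees. It gave 19% and 30% for within-patient ICC 0.05 and 0.10 with 26 records. For clinic ICC 0.01 it gave 49% with 26 records per patient and 7.5% with one.

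**6. What each unit of analysis would mean.**
- *Pooled biweekly records:* repetition within patient and clinic is ignored, as in the table.
- *Clinic totals of alerts or follow-ups:* each event counts as independent, although one child can produce many.
- *One summary per patient against a clinic characteristic:* repetition is gone, but clinic correlation remains.
- *A separate test each round:* clinic correlation remains, with up to 26 tests and no multiplicity rule.
- *One record per clinic:* n is 4 or 5. For a binary outcome, the smallest two-sided exact p-value is 1/10 = 0.10 with five clinics split 2 v 3, and 1/4 = 0.25 with four split 1 v 3.
- *One summary per patient against clinic identity:* roughly valid, because clinic is then the factor compared.

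**The case against.** The SAP never says that each biweekly record enters the test as a separate observation. A yearly summary per patient would fit its wording and remove the repetition. The data are described as coming from clinics, so they may be totals, and repetition within patients is an inference. If a clinic predictor means clinic identity, variation between clinics is the effect of interest and not a nuisance. Flags and calls follow over- or underuse, so a record for every child in every round is an upper limit. A SAP test that goes beyond the Protocol's descriptive plan is not invalid for that reason alone.

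All of this stands as a limit on size. It does not remove the point, because only one of the units of analysis listed above makes the test roughly valid, and the SAP does not specify that one.

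A reader might go further and infer that the p-values are certainly far too small, that the effective sample size is simply four or five, or that 47% is the error rate to expect. Each needs an ICC, a unit of analysis or a meaning of clinic predictor that the documents do not supply. A reader might also infer that these tests drive a roll-out decision. The Protocol says only that feasibility of wider implementation will be assessed and that the team will help prepare for roll-out if applicable. It does not link that to Aim 3 p-values.

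**Conclusion.** The point holds in conditional form. The SAP names a test that requires independence for data that are repeated over time and clustered in four or five clinics. It states neither the unit of analysis nor an adjustment, and it departs from the Protocol's descriptive plan. If biweekly records are pooled, the p-values are too small under any positive correlation.

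The size is open: from no inflation at zero correlation, through about 8% to 30% for repetition within patients, to about 47% for a clinic-level predictor on pooled records at an assumed clinic ICC of 0.01. With one record per patient and the same clinic ICC, it is about 8%. These figures rest on the assumed ICCs, 26 rounds, equal clinics and a two-level predictor; a comparison across clinic identities has more degrees of freedom and would give other values.

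The consequence is limited. This is a secondary process measure with no stated significance level, and the primary outcomes are unaffected. The SAP should be changed, but the trial's main conclusions do not depend on it.

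**What to change.** Reconcile the two documents by dropping the chi-squared test on dashboard data from SAP Aim 3. Report alerts, follow-ups and follow-up outcomes descriptively by clinic, as the Protocol plans.

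If associations are wanted, the SAP should:
- state the unit of analysis and define the clinic predictors;
- use one summary per patient, or a GEE or mixed model (logistic or count, to suit the outcome) with patient as cluster and clinic as a fixed effect;
- treat any clinic-level characteristic as descriptive, because four or five clinics cannot support reliable inference on it.

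The cost is a change of SAP wording and fewer p-values in a secondary feasibility aim. Data collection does not change.

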| Parent-reported values (un-validated) | School days missed due to asthma | 5 times in total (baseline, 3 months, 6 months, 9 months, study completion) |
| Pediatric Caregiver Asthma-related Quality of Life Questionnaire (PACQLQ) | Parent form of how their child's asthma is affecting both their lives and the life of their child | 5 times in total (baseline, 3 months, 6 months, 9 months, study completion) |

Parental Management Outcomes

| Source | Outcome | Time Point |
|-----------------------------------|--|---|
| Parent report (Survey) | Feasibility and acceptability of Platform | 5 times in total (baseline, 3 months, 6 months, 9 months, study completion) |
| Remote Health Management Platform | Frequency of use of the application (synching) | Monthly data pull |

Physician and Clinical Team Outcomes

| Source | Outcome | Time Point |
|-----------------------------------|---|---|
| Remote Health Management Platform | ICS and SABA use | Monthly download |
| Web Portal/Epic | Asthma-related ED visits, hospitalizations, and oral corticosteroid prescriptions/courses | Monthly Epic data pull |
| Clinician Survey | Feasibility and acceptability of the Platform | 1 month into the study, 6 months and study completion |
| Physician Survey | Feasibility and acceptability of the Platform | 1 month and study completion |
| Remote Health Management Platform | Frequency of use of the web portal | Monthly data pull |

Data Analysis:

Primary Outcomes

- *ACT*: Parent-reported test on their child's asthma control
- *Asthma-related hospitalizations*: Data will be obtained from the EMR and parent report.
- *Asthma-related ED visits*: Data will be obtained from the EMR and parent report.
- *Asthma-related oral corticosteroid use*: Prescription/course data will be obtained from the EMR and parent report.

Secondary Outcomes

- *Inhaler Use*: Use data, including frequency of both SABA and ICS inhalers, will be obtained via the sensor throughout the study period.
- *PAMSE*: Parental Asthma Management Self-Efficacy; self-report survey that measures parental self-efficacy for the management and prevention of acute exacerbations of asthma.
- *PACQLQ*: Paediatric Asthma Caregiver's Quality of Life Questionnaire; will assess the impact of their child's asthma on their lives, the lives of their children with asthma, and the family as a whole.

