4. In the past week, how many alerts did you receive due to patients overusing albuterol?
 - One
 - Two

- 3 or more
- 5. In the past week, how many times did you have to follow-up with patients regarding their underuse of their controller medication?
 - Once
 - Twice
 - 3 or more times
- 6. In the past week, how many alerts did receive due to patients underusing their controller medication?
 - One
 - Two
 - 3 or more
 - Zero
- 7. On a scale of 1-5 (1 being the least helpful, and 5 being the most helpful), how helpful do you feel calls to patients improve asthma management?
 - 1
 - 2
 - 3
 - 4
 - 5
- 8. On a scale of 1-5 (1 being the least useful, and 5 being the most useful) how much do you think the parents found your call useful?
 - 1
 - 2
 - 3
 - 4
 - 5

Qualitative Questions:

1. What do you find useful about the Propeller dashboard?
2. What changes do you think are needed to improve the Propeller dashboard?
3. How are you currently using the Propeller dashboard? Please describe.
4. Would you utilize the Propeller health management platform for your current practice in the future?

Sample Size Determination:

Assuming asthma exacerbation rate of 0.545 for the intervention arm, and asthma exacerbation rate of 0.75 for the standard treatment arm, resulting odds ratio (OR) equal to 0.3992674, and $\log(\text{OR}) = -0.9181239$. Assuming 20% patient drop-out rate, two-sided significance level $\alpha = 0.05$, a total of 250 patients (125 per arm) is needed in order to achieve a statistical power of 85%. The sample size calculation was computed using SAS procedure PROC SEQDESIGN.

Qualitative Analyses of Semi-Structured Interviews:

Data will be analyzed systematically using a constant comparative approach; and four analysts (i.e., coders), including [name] (qualitative methods expert), [name], and 2 research team members, will meet to discuss initial thoughts, insights, and observations for the development of initial coding categories (e.g., themes). Through a systematic analysis process, themes will be continually refined by collapsing redundant themes and removing irrelevant themes. Once no new categories have emerged, a

codebook will be developed for the remaining analysis. We will construct a saturation grid, to track themes as they emerge and determine when no new information is obtained

Study Staff:

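### Aim 3 gives no denominator for alert, follow-up and portal-use counts, so unadjusted summaries and clinic comparisons mix clinician behaviour with the number of children on the platform

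*SAP*

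**What the plan says.** **Dashboard data.** The SAP's Aim 3 section collects, every two weeks from clinics, how often physicians follow up and with what result. It also counts the alerts physicians receive. The analysis sentence is: "The data from the Propeller dashboard will be summarized and associations between outcomes and clinic predictors will be analyzed by Chi-squared test". The protocol's own Aim 3 text plans only descriptive statistics for these data.

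**Clinician survey.** Items 1 and 3 to 6 in the protocol's Aim 3 questions are counts over the past week. Item 4, for example, asks: "In the past week, how many alerts did you receive due to patients overusing albuterol". The top answer category is three or more. The SAP tabulates survey answers at each time point and tests them by chi-squared against clinic predictors.

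**Timing.** The SAP surveys clinicians at 1, 3, 6, 9 and 12 months without saying from what date. The protocol's table of physician and clinical team outcomes dates the clinician survey by study time: "1 month into the study, 6 months and study completion". Enrolment runs "December 2016-December 2017" (protocol, Timeline, Phase 1), and each intervention child has the device for one year (Phase 2).

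**Portal use.** The same outcomes table lists frequency of web portal use, from a monthly data pull.

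**A partial counter-indication.** Under Secondary Outcomes, the protocol's clinical management entry speaks of rates of follow-up over a year for each intervention participant, then says the measure is a count of completed tasks. It defines no rate, and the Aim 3 analysis text does not take one up.

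**The concern.** A clinician's alerts, follow-up calls and reasons to open the dashboard depend on how many of that clinic's children have a working sensor that week. That number changes as children enrol and finish, and it may differ between clinics. A raw count is the product of caseload and per-child activity, and the plan does not separate the two.

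The protocol's Aim 3 asks whether the platform is feasible and sustainable for the healthcare team, and the Study Extension section says wider implementation will be assessed. Caseload growth could then be read as growing engagement, the later emptying of the platform as fading engagement, and a clinic predictor that follows clinic size as a cause of good follow-up. By contrast, Aim 1 of the same SAP defines 12-month rates and uses negative binomial regression for its counts.

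**Working it through.** **1. Number of intervention children.** Aim 3 has no computed figure of its own. The only design figure is the sample size, which supplies the 125 children used below. The protocol starts from "Assuming asthma exacerbation rate of 0.545 for the intervention arm, and asthma exacerbation rate of 0.75 for the standard treatment arm". Its other inputs are an odds ratio of 0.3993 (log −0.9181), two-sided alpha 0.05, 85% power and 20% drop-out. A Wald test on the log odds ratio gives, per arm:

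(1.960 + 1.036)² × [1/(0.545 × 0.455) + 1/(0.75 × 0.25)] / 0.9181² = 99.8, so 100.

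Then 2 × 99.76 / 0.80 = 249.4, so 250 in total and 125 per arm. The stated figure reproduces.

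**2. Children on the platform.** Assume even accrual over 12 months and one year on the device. The census at month t ≤ 12 is 125 × t/12. After month 12 it falls by the same amount each month. The 10 pilot children also keep the device for a year and are counted here through month 11.

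| Month | Trial children | With pilot children |
|---|---|---|
| 1 | 10.4 | 20.4 |
| 3 | 31.2 | 41.2 |
| 6 | 62.5 | 72.5 |
| 9 | 93.8 | 103.8 |
| 12 | 125 | 125 |
| 18 | 62.5 | 62.5 |
| 24 | 0 | 0 |

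- Months 1 to 12: 125/10.4 = 12-fold; with the pilot children, 125/20.4 = 6.1-fold.
- The protocol's Gantt table marks Year 1 recruitment over 8 months. On that basis the census is 125/8 = 15.6 at month 1 and 125 from month 8: an 8-fold rise, then a plateau.
- Drop-out lowers these ratios. If the full 20% had left by month 12 and none by month 1, they would be 100/10.4 = 9.6 and 100/20.4 = 4.9.
- If follow-ups per child halved between months 1 and 12, the raw count would still rise 12 × 0.5 = 6-fold, or 6.1 × 0.5 = about 3-fold with the pilot children.

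**3. Effect on a survey item.** Assume five equal clinics, one clinician receiving all of a clinic's alerts, and Poisson alerts at a constant 0.1 per child-week. With mean m, P(3 or more) = 1 − e^(−m)(1 + m + m²/2).

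- Month 1: m = 0.21, P = 0.1%.
- Month 6: m = 1.25, P = 13%.
- Month 12: m = 2.5, P = 46%.

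The month-12 value is 1.4%, 13% and 88% at 0.02, 0.05 and 0.2 alerts per child-week. It is lower if several clinicians share a clinic's alerts.

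**4. Effect on a clinic comparison.** Alerts were simulated 20,000 times with identical per-child rates in every clinic, then tested at 5% for equal totals across clinics. This illustrates a test on raw counts; the SAP does not specify its table.

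| Children per clinic | Raw counts, 0.5 alerts per child-year | Raw counts, 2 alerts per child-year | Expected counts proportional to children |
|---|---|---|---|
| 25 in each of 5 | 4.9% | 4.8% | 4.8–4.9% |
| 20/22/25/28/30 | 12% | 44% | 4.8–5.0% |
| 10/15/25/30/45 | 90% | 100% | 5.0% |
| 10/20/35/60 | 99% | 100% | 4.8–5.1% |

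A chi-squared test of the share of alerts followed up, with an equal true share in every clinic, rejected 4.8–5.1% of the time at all these sizes.

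**The case against.** A reader might infer that the plan deliberately analyses per clinician and not per child, that rolling enrolment alone produces the time trend, and that clinic size determines the clinic comparisons. The documents support none of these as stated.

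- **Not per child** would be read from silence. The clinical management outcome refers to rates over a year for each intervention participant. What stands is that the denominator is undefined and the two texts are not reconciled.
- **Time trend.** No trend test is planned, and the summary at each time point is stated for the surveys only. Real changes in alerts, use or drop-off would add to the census effect. A steady rise also depends on the clock: on the outcomes table's schedule, with completion taken as the end of Phase 2 (about month 24), the census is about 10, then 63, then 0. That removes a uniform rise but not the confounding.
- **Clinic comparisons.** Bias needs unequal clinics and a test on counts or count categories. A chi-squared test suits follow-up outcome per alert well, and that table is sound. For the dashboard data the SAP does not say which table is meant. For the survey items, however, it does plan to test answers that are themselves counts.
- **Workload.** Total alerts and calls per clinician are a legitimate measure of burden on staff. This stands, so totals should be kept.
- **Importance.** Aim 3 is process data. This limits the weight of the point, but the results are meant to inform wider use.

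**Conclusion.** The concern holds in a limited form. Aim 3 names no denominator, offset or count model for alerts, follow-ups or portal use, and the survey items tested against clinic predictors are raw weekly counts. Followed literally, the plan mixes caseload with clinician behaviour. The census changes roughly 6- to 12-fold over months 1 to 12 under even 12-month accrual, depending on whether the pilot children are counted; drop-out would reduce this somewhat. Accrual pattern, clinic sizes, alert rates and one clinician per clinic are assumptions, since the documents give none of them. The rejection rates show what a test on raw counts could do, not what the SAP's test will do. Follow-up outcome per alert is unaffected, as are the primary outcomes and the randomised comparison.

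**What to change.** In the SAP's Aim 3 section, and in the matching protocol text:

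1. Reconcile the Aim 3 analysis with the protocol's clinical management outcome, and define the follow-up rate once.
2. Keep total counts, labelled as workload. Beside them report alerts per active child-week, portal use per active child-month and follow-ups as a proportion of alerts, by clinic and period. Define an active child and say whether pilot children count.
3. Where alerts or portal use are tested against clinic predictors, replace chi-squared on counts with a count model using log(active child-time) as offset.
4. For follow-ups, use a binomial model of alerts followed up out of alerts received, excluding clinic-periods with none. A log(alerts) offset would not work: at 2.08 children per clinic and 0.1 alerts per child-week, e^(−0.208) = 81% of clinic-weeks have no alert, and the offset is then undefined.
5. Label these tests exploratory, given clustering by clinic and perhaps only four or five clinics.
6. Show survey count items next to the number of active children at that clinic, state the date from which survey months run, and do not read the raw trend as a change in engagement.

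The cost is SAP wording and a little more analysis. The denominators come from enrolment, sensor and dashboard data that the trial already collects.
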